Participant Recruitment, Screening and Randomization:

CC's Center for Neurological Restoration (CNR) manages 6,000+ PD patients; each patient typically has semi-annual neurology visits which include a complete MDS-UPDRS III evaluation. UU's Movement Disorders Program manages 2,000+ PD patients. Their respective Directors, Drs. [name] (Cleveland) and [name] (Utah), will lead their medical teams to screen in recruiting for this project and will complete MDS-UPDRS III clinical evaluations, blinded to group assignment. The pragmatic clinical trial design, with exercise at home and relatively few visits to the study site, will minimize travel burden, easing recruitment and facilitating recruitment of a racially and socio-economically diverse patient group.²³ It is anticipated that study sites will enroll an equal number of participants. Adults with idiopathic PD who meet inclusion criteria and cleared for exercise will

be randomized to either the home exercise or UCC group, using a permuted block randomization stratified by site, with random block sizes of 8, 10, or 12 for the first 8 blocks at each site, and 4, 6, or 8 subsequently, preloaded into a secure and shared RedCap electronic data management system developed at CC. Both sites have effectively utilized RedCap across in previous multi-site clinical trials,²⁴⁻³¹ and clinical programs. Figure 1 depicts study flow. Total study participation time is projected to be 12.5 months, including ~2.5 weeks for cycle delivery and completion of initial Comprehensive Assessments (On-/Off- meds).

As shown in Figure 1, three Comprehensive assessments of motor and non-motor function will be conducted for all participants. Comprehensive (90 mins) assessments (Table 1) will be overseen by Drs. [name] and [name], and will be completed at project enrollment (On- and Off-medication), 6 months (Off-medication), and 12 months (Off-medication). Visit windows will be within \pm 10 days of their nominal dates. Participants will be reimbursed for time and travel expenses of \$50 for each assessment. All clinical and self-report data will be entered into the RedCap database (see Data and Safety Monitoring). Each site's biomechanical data from the iPad will be uploaded securely, with encryption, to the CC HIPAA-compliant cloud instance (ClearData), processed in the cloud, and integrated into the [name] lab's on-premises, firewall protected, server.

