Asking participants to withhold medication for Off-state examinations imposes a burden, but the Off-state (12 hours off meds) will increase insight into the direct effect of exercise on PD itself. Since medication changes are frequent with PD and often result in symptomatic fluctuations, the Off-state provides a more reliable, less confounded time comparisons. Medication reconciliation will be completed at each examination, and levodopa equivalent daily doses (LEDDs) will be determined and utilized in the prediction model (Aim 4). To determine the potential impact of overall physical activity in disease progression, all patients will be provided a Garmin activity monitor to measure overall daily activity (e.g., active minutes and steps per day). Currently, the Garmin activity monitor is utilized by 30,000+ participants in the CC Health System employee health plan, and accurately counts steps and activity levels of individuals with PD.³² Patients will wear the device on their belt/waistband or shoe during waking hours and upload the data every 30 days via the supplied application. Device batteries typically last ~6-months. To ensure no loss of data the battery will be replaced at the 6 month assessment. Activity monitor data will be synchronized with the secure CC Health system portal and downloaded to the [name] research server behind the CC firewall. The number of steps and minutes of activity, binned by day, week, month and year, will be considered for inclusion in the predictive model in Aim 4.

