Title: Pragmatic Cyclical Lower Extremity Exercise Trial for
Parkinson's Disease

NCT#: NCT04000360

Document Date: January 29, 2024

The Cyclical Lower Extremity Exercise for Parkinson Disease II (CYCLE-II) Study
Principle Investigator: [name].
Site Principal Investigator: [name].

Statistical Analysis Plan: Assessment of Treatment Effect
Study Statistician: [name].

Overview

CYCLE-II is a pragmatic two center, blinded examiner, 1:1 randomized clinical trial to assess whether one year of a home Peloton-cycle based aerobic exercise regimen alters Parkinson's disease progression from that of patients receiving usual care and usual physical activity. The trial is conducted at the Cleveland Clinic and the University of Utah, coordinated by the former. The CYCLE-II study design and basic analytic plan have been published (*Phys Ther* 2021 Nov; 101(11):pzab191, PMCID: PMC8632855). Multiple prespecified quantitative outcomes are hierarchically classified as primary inferential, secondary inferential, and descriptive exploratory outcomes, and assessed in randomly ordered on and off Parkinson's medication examinations at baseline, and again off medication at six and 12 months. Parkinson's disease progression is to be assessed in each group by the estimated annual rates of change of off-medication outcome measures, and the treatment groups are to be compared in intention-to-treat analyses of these estimates.

Study Outcomes

The primary outcome is the total score on the Movement Disorder Society Unified Parkinson's Disease Rating Scale Part III: Motor Examination, an assessment of the motor signs of Parkinson's disease by an examiner masked to the participant's treatment group. Secondary inferential motor outcomes are:

- i. Upper extremity dexterity: time to complete a iPad-based modification of the Nine Hole Peg Test;
- ii. Lower extremity functional mobility
 - a. time to complete an iPad-instrumented Time Up and Go Test;
 - b. average turn velocity on an iPad-instrumented Time Up and Go Test;
- iii. Ambulation gait speed
 - a. average "comfortable speed" velocity on the Ten Minute Walk Test;
 - b. average "fast speed" velocity on the Ten Minute Walk Test;

Secondary non-motor outcomes are:

- i. Neural processing speed: number correct on the New Processing Speed Test;
- ii. Episodic visual memory: Number of locations + number of symbols correctly recalled on the New Symbol Modalities Test;

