In inferential analyses we will presume that missing observations, for whatever reason they may be missing, are technically “missing at random,” i.e., that the unobserved data come from the same distributions, conditional on other variables that have been ascertained in CYCLE II, as do the observed data. Under this assumption, we will multiply impute missing data using both baseline variables and outcome data and will include the multiply imputed outcome data in analyses. Specifically, missing data will be multiply imputed by sequential chained equations using fully conditional specification and the following sets of predictors:

- i. baseline sociodemographic and other characteristics: age, sex, race, ethnicity, residential living situation (alone, with family member or friend, with significant other), employment status (full-time, part-time, retired due to Parkinson's disease related disability, otherwise retired), body mass index (BMI), hand dominance;
- ii. baseline exercise habit: current regular exercise (yes/no), regular aerobic, resistance, and flexibility exercise (yes/no to each), regular home, gym, and outdoor exercise (yes/no to each), exercise intensity;
- iii. Parkinson's disease-related factors: years since diagnosis, leva dopamine equivalent dose, primary Parkinson's disease symptom, patient-reported past year fall count (0, 1-2, 3-12, 13+);
- iv. CYCLE-II characteristics: clinical site, randomized group;
- v. concurrently measured primary and secondary (motor and non-motor) outcomes;
- vi. the same outcome at other visits.

Variables will be imputed by forward order in time with the primary outcome last within each time. At least 25 imputations will be obtained, and trace plots for the primary outcomes will be checked for evident departures for convergence, with burn-in iterations increased until stationarity appears to have been achieved.

Baseline description

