The distributions of baseline variables will be summarized, overall and by treatment group, by frequency distribution for dichotomous and other categorical factors, mean and standard deviation for reasonably symmetrically distributed quantitative variables, and Tukey five-number summaries (median, quartiles, extrema) for substantially skewed variables. We will also examine boxplots, histograms and kernel density estimators for continuous variables, and use standardized mean differences for continuous variables and categories of nominal and ordinal variables to describe balance of the randomized treatment groups.

Outcome description and distributional assessment

All prespecified outcomes are quantitative or potentially treatable as such depending on the degree to which their full scales occur in our study population. We will thus describe each initially as indicated above for quantitative baseline variables, overall and by treatment \times time combinations, including visually using grouped boxplots and kernel density estimators. To assess compatibility with the assumptions of the planned analytic approach, for each outcome we will use restricted (equivalently, residual) maximum likelihood (REML) estimation to fit preliminary mixed models with fixed effects of randomized treatment, visit, and their interactions, and with unrestricted covariance matrices -- thus allowing within treatment and visit variability to change over time and accounting for arbitrary correlations between measurements of the outcome in the same patient at different visits. These models will not be used to estimate treatment effects, but only to assess the compatibility of their residuals with the requisite distributional assumptions about random noise to support validity of fixed effect estimates and tests from the planned inferential analyses.

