For outcomes with distributional characteristics reasonably compatible with standard linear mixed model assumptions, we will employ prespecified linear mixed model analyses for the observations at baseline, six months, and twelve months, i.e., one year, as described below. For outcomes whose distributions, conditional on treatment and time, are substantially skewed and/or lighter or heavier tailed than Gaussian distributions (leptokurtotic or platykurtotic), we will consider applying the planned analysis to a Box-Cox and other reasonably straightforward data transformation of the outcome and backtransforming the results, and/or use of a generalized linear mixed model with log or other link function and/or a non-Gaussian exponential family or a beta error distribution. In exploring Box-Cox transformations, we will be generally guided by the independence pseudologlikelihood of the fitted fixed effects model saturated for treatment \times visit with clinical site as an additive covariate, as a function of the Box-Cox transformation power parameter. If and when transformations are used, we will report modeling results on the transformed scale and also report additive treatment effects, which for nonlinear transformations will vary by baseline value of the outcome, for selected percentiles of such baseline values. Nonparametric approaches such as quantile regression or product multinomial-based mixed categorical data models for marginal means will be considered as needed for bounded integer-scored outcomes with limited ranges and/or floor or ceiling effects, which may not admit of straightforwardly interpretable and communicable normalizing transformations.

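### The SAP gives the On-medication baseline scores no stated role; conditioning on both the Off and On baselines could modestly narrow the treatment contrasts

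*Protocol*

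**What the plan says.** **Who is examined, and when.** The protocol (Participant Recruitment, Screening and Randomization) states that "three Comprehensive assessments of motor and non-motor function will be conducted for all participants", at "project enrollment (On- and Off-medication), 6 months (Off-medication), and 12 months (Off-medication". The SAP Overview agrees: outcomes are "assessed in randomly ordered on and off Parkinson's medication examinations at baseline, and again off medication at six and 12 months".

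**What is analysed.** Progression is measured by "estimated annual rates of change of off-medication outcome measures". The protocol's reason is that "the Off-state provides a more reliable, less confounded time comparisons".

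**The model.** The SAP plans "prespecified linear mixed model analyses for the observations at baseline, six months, and twelve months". The preliminary models carry "fixed effects of randomized treatment, visit, and their interactions, and with unrestricted covariance matrices". The treatment-effect models (Treatment effect estimation and testing) refer back to these, with time made linear. The natural reading is one Off baseline record per patient, treated as an outcome, with a separate baseline mean in each arm and no baseline covariate.

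**Where On scores could appear.** Missing Data item v lists outcomes measured at the same visit, and item vi lists "the same outcome at other visits"; neither names a medication state. Sensitivity analyses adjusts for listed baseline variables that turn out to be imbalanced, and Effect modification/subgroup analyses lists its own variables. Neither list mentions an On score. No passage in either document says what the On exam is for.

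**The concern.** Every participant sits a second full baseline battery, and nothing says how its results will be used. For each outcome, the On score is a further baseline reading of the same patient. Together with the Off score it can help separate the patient's underlying level from error in a single Off exam. If it is measured before randomization, using it as a covariate leaves the randomized comparison intact.

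What is at stake is the precision of the nine inferential contrasts, and clarity: from items v and vi as written, two programmers could build different imputation models.

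**Working it through.** **1. What can be reproduced.** The nine inferential outcomes check: 1 primary + 5 motor + 3 non-motor. The target of about 250 cannot be reproduced, because the documents give no effect size, SD, correlation, power or dropout rate. Every variance below is therefore an assumption; only the 1:1 allocation, the total of about 250 (125 per arm) and the three equally spaced visits come from the plan.

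**2. Assumed structure** (Off baseline variance = 1, t in years).
- Off at time t = T + D·t + e_t, with Var(T) = 0.85 (the reliability), Var(D) = 0.15, Var(e) = 0.15.
- On at baseline = λT + r + e_on, with Var(e_on) = 0.15.
- Drug-responsive motor example: λ = 0.65, SD(r) = 0.40. Var(On) = 0.65² × 0.85 + 0.16 + 0.15 = 0.669.
- Little drug response: λ = 1, SD(r) = 0.15. Var(On) = 0.85 + 0.0225 + 0.15 = 1.0225.

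**3. Planned model.** With three equally spaced visits the slope is Off12 − Off0. Its variance is 0.15 + 0.15 + 0.15 = 0.45. SE of the contrast = √(2 × 0.45/125) = 0.0849.

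**4. Planned model plus On.** Off12 − Off0 = D + e12 − e0, which is uncorrelated with On when errors are independent, so the SE stays at 0.0849. In 4,000 simulated trials under a different assumed structure (Off correlation 0.8, On–Off correlation 0.7), adding On as a main effect left the slope contrast identical to machine precision, and an On × time term did not help (0.0800 against 0.0802). If On and Off errors correlate 0.5, an On × time term in the motor example removes only about (0.5 × 0.15)²/(0.669 × 0.45) = 1.9% of variance.

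**5. Off baseline constrained equal across arms.** The fitted baseline is a = (5·Off0 + 2·Off6 − Off12)/6. Var(a) = 0.85 + 0.15 × 30/36 = 0.975, and Cov(a, slope) = −0.15. Residual variance = 0.45 − 0.15²/0.975 = 0.4269; SE 0.0826. This saves 5.1% and needs no On data.

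**6. Adding On to step 5** (independent errors). Residual variance = 0.45 − 0.0225/[0.975 − (0.85λ)²/Var(On)].
- Motor: 0.45 − 0.0225/(0.975 − 0.4562) = 0.4066; SE 0.0807.
- Little drug response: 0.45 − 0.0225/(0.975 − 0.7066) = 0.3662; SE 0.0765.

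**7. Correlated On and Off baseline errors** (a shared rater or patient state), by generalised least squares on the full covariance:

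| Example | Error correlation | SE with both baselines | On itself adds | Both, against planned |
|---|---|---|---|---|
| Motor | 0 | 0.0807 | 4.8% | 9.6% |
| Motor | 0.3 | 0.0820 | 1.6% | 6.6% |
| Motor | 0.5 | 0.0825 | 0.3% | 5.4% |
| Little drug response | 0 | 0.0765 | 14.2% | 18.6% |
| Little drug response | 0.3 | 0.0787 | 9.2% | 13.9% |
| Little drug response | 0.5 | 0.0801 | 6.2% | 11.0% |

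**8. Wider assumptions.** With reliability 0.75–0.92, Var(D) 0.05–0.30 and independent errors, the formulas in steps 5 and 6 give an On contribution of about 2–7% (motor) and 7–19% (little drug response). If Off scores follow AR(1) and On relates to later Off scores only through the observed Off baseline, On adds exactly 0%.

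**9. On used only as an imputation auxiliary.** With an assumed 15–20% of 12-month scores missing and the planned model kept, variance falls by 0.1–2.6%.

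**10. In power terms.** From 80%, a variance saving s gives Φ(2.802/√(1 − s) − 1.960): 82% at s = 5%, 85% at 12%, 88% at 20%.

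**The case against.** The case against is substantial, and much of it stands.

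- *The planned model cannot use On.* Correct (step 4). A reader might infer that putting On into the existing model would sharpen all nine contrasts; it would not. The benefit requires conditioning on baseline, which is a change to the model form, and part of it (5.1% here) comes from the Off baseline alone.
- *The gain rests on assumed correlations.* Correct. The documents give none, error correlation of 0.5 removes nearly all of the On contribution in the motor example, and one plausible structure gives zero. On scores also carry drug response, so they are not replicates of the Off score. Nothing in the documents shows that the cognitive tests respond little to medication.
- *On scores may be used after all.* A reader might infer that they are excluded from imputation or discarded altogether. The documents do not support that. Items v and vi leave the medication state open, and Aim 4 draws on baseline disease status, which could include On scores. The SAP's title limits it to treatment effects. Aim 4, however, is a prediction model within the exercise cohort and does nothing for the randomized contrasts.
- *On may not be a pre-randomization value.* The protocol places cycle delivery and the initial On/Off assessments in the same period of about 2.5 weeks, and the SAP's Analysis Sets speaks of randomized patients completing baseline procedures. The order must be confirmed before On is used as a covariate.

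What remains is that no role is stated for data collected from everyone, and that a low-cost precision gain is available. The existing adjusted sensitivity analysis will not supply it, because covariates enter there only on observed imbalance and On scores are not among the listed variables.

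**Conclusion.** The point holds as one of efficiency and clarity. At reliability 0.85 and change variance 0.15, using both baselines in a model that conditions on baseline cuts slope-contrast variance by about 5–10% for drug-responsive motor outcomes and 11–19% for outcomes with little drug response. On itself accounts for about 0–5% and 6–14% respectively; the low ends apply when On and Off errors correlate 0.5. The gain for the primary outcome is probably small, if MDS-UPDRS III behaves like the drug-responsive example. Whether any secondary outcome falls in the second group is not known from the documents.

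A reader might take the omission as a source of bias. It is not: the planned Off-only comparison is valid as it stands, and the protocol gives a reason for choosing the Off state.

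**What to change.** 1. Confirm, and state in the SAP, that the On exam precedes randomization. State what the On scores are for.
2. In Treatment effect estimation and testing, or at least as a prespecified adjusted analysis under Sensitivity analyses, model the 6- and 12-month Off scores with the Off and On baseline values of the same outcome as covariates, each crossed with time. Write the treatment effect so that it is zero at baseline and still estimates a difference in annual rates. Alternatively, keep the three-visit model, constrain the Off baseline to be equal across arms and add the On baseline; this also yields the within-arm rates directly. Enter On on the same scale as the analysed outcome.
3. In Missing Data, name the baseline On values of the primary and secondary outcomes as predictors, and give the medication state in items v and vi.

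Cost: a small change to the model form, one or two extra covariates per outcome, and a few On values to impute. No new data are needed. The choice should be fixed without reference to results by arm.

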Title: Pragmatic Cyclical Lower Extremity Exercise Trial for
Parkinson's Disease

NCT#: NCT04000360

Document Date: January 29, 2024

The Cyclical Lower Extremity Exercise for Parkinson Disease II (CYCLE-II) Study
Principle Investigator: [name].
Site Principal Investigator: [name].

Statistical Analysis Plan: Assessment of Treatment Effect
Study Statistician: [name].

Overview

CYCLE-II is a pragmatic two center, blinded examiner, 1:1 randomized clinical trial to assess whether one year of a home Peloton-cycle based aerobic exercise regimen alters Parkinson's disease progression from that of patients receiving usual care and usual physical activity. The trial is conducted at the Cleveland Clinic and the University of Utah, coordinated by the former. The CYCLE-II study design and basic analytic plan have been published (*Phys Ther* 2021 Nov; 101(11):pzab191, PMCID: PMC8632855). Multiple prespecified quantitative outcomes are hierarchically classified as primary inferential, secondary inferential, and descriptive exploratory outcomes, and assessed in randomly ordered on and off Parkinson's medication examinations at baseline, and again off medication at six and 12 months. Parkinson's disease progression is to be assessed in each group by the estimated annual rates of change of off-medication outcome measures, and the treatment groups are to be compared in intention-to-treat analyses of these estimates.

Study Outcomes

The primary outcome is the total score on the Movement Disorder Society Unified Parkinson's Disease Rating Scale Part III: Motor Examination, an assessment of the motor signs of Parkinson's disease by an examiner masked to the participant's treatment group. Secondary inferential motor outcomes are:

- i. Upper extremity dexterity: time to complete a iPad-based modification of the Nine Hole Peg Test;
- ii. Lower extremity functional mobility
 - a. time to complete an iPad-instrumented Time Up and Go Test;
 - b. average turn velocity on an iPad-instrumented Time Up and Go Test;
- iii. Ambulation gait speed
 - a. average "comfortable speed" velocity on the Ten Minute Walk Test;
 - b. average "fast speed" velocity on the Ten Minute Walk Test;

Secondary non-motor outcomes are:

- i. Neural processing speed: number correct on the New Processing Speed Test;
- ii. Episodic visual memory: Number of locations + number of symbols correctly recalled on the New Symbol Modalities Test;
- iii. Working memory/set switching: the ratio of time to complete the Trail Making Test B to time to complete the Trail Making Test A.

Descriptive/exploratory motor outcomes are:

- i. Cardiovascular fitness: Six Minute Walk Test distance;
- ii. Postural stability:
 - a. Balance Error Scoring System (BESS) double leg area
 - b. Balance Error Scoring System (BESS) tandem area
 - c. Balance Error Scoring System (BESS) double leg volume
 - d. Balance Error Scoring System (BESS) tandem volume
- iii. Total self-reported falls during the one-year observation period.

Descriptive/exploratory non-motor outcomes are:

- i. Movement Disorder Society Unified Parkinson's Disease Rating Scale Part I: Non-Motor Aspects of
- ii. Experiences of Daily Living (nM-EDL)
- iii. Movement Disorder Society Unified Parkinson's Disease Rating Scale Part II: Motor Aspects of Experiences of Daily Living (M-EDL)

iv. Movement Disorder Society Unified Parkinson's Disease Rating Scale Part IV: Motor Complications. The latter two scales are classified as non-motor rather than motor outcomes because they focus on patient-reported experience of functional and social impacts of the effects of motor symptoms rather than on the symptoms themselves.

Analysis Sets

The inferential and safety analysis set will consist of all randomized patients. The descriptive/exploratory analysis set will consist of all randomized patients who complete baseline procedures for initiating randomized treatment and follow-up, and for whom study follow-up is initiated. Descriptions of baseline variables will use all available data in the inferential and safety analysis set. Inferential and safety outcomes will be analyzed using the inferential and safety analysis set in accordance with the strict intention-to-treat principle, under which all randomized patients are included in analyses in accordance with their randomized treatment assignments, regardless of their post-randomization experience including treatment and dropout from treatment or study. Descriptive/exploratory outcomes will be analyzed using the descriptive/exploratory analysis set.

Missing Data

In inferential analyses we will presume that missing observations, for whatever reason they may be missing, are technically “missing at random,” i.e., that the unobserved data come from the same distributions, conditional on other variables that have been ascertained in CYCLE II, as do the observed data. Under this assumption, we will multiply impute missing data using both baseline variables and outcome data and will include the multiply imputed outcome data in analyses. Specifically, missing data will be multiply imputed by sequential chained equations using fully conditional specification and the following sets of predictors:

- i. baseline sociodemographic and other characteristics: age, sex, race, ethnicity, residential living situation (alone, with family member or friend, with significant other), employment status (full-time, part-time, retired due to Parkinson's disease related disability, otherwise retired), body mass index (BMI), hand dominance;
- ii. baseline exercise habit: current regular exercise (yes/no), regular aerobic, resistance, and flexibility exercise (yes/no to each), regular home, gym, and outdoor exercise (yes/no to each), exercise intensity;
- iii. Parkinson's disease-related factors: years since diagnosis, leva dopamine equivalent dose, primary Parkinson's disease symptom, patient-reported past year fall count (0, 1-2, 3-12, 13+);
- iv. CYCLE-II characteristics: clinical site, randomized group;
- v. concurrently measured primary and secondary (motor and non-motor) outcomes;
- vi. the same outcome at other visits.

Variables will be imputed by forward order in time with the primary outcome last within each time. At least 25 imputations will be obtained, and trace plots for the primary outcomes will be checked for evident departures for convergence, with burn-in iterations increased until stationarity appears to have been achieved.

Baseline description

The distributions of baseline variables will be summarized, overall and by treatment group, by frequency distribution for dichotomous and other categorical factors, mean and standard deviation for reasonably symmetrically distributed quantitative variables, and Tukey five-number summaries (median, quartiles, extrema) for substantially skewed variables. We will also examine boxplots, histograms and kernel density estimators for continuous variables, and use standardized mean differences for continuous variables and categories of nominal and ordinal variables to describe balance of the randomized treatment groups.

Outcome description and distributional assessment

All prespecified outcomes are quantitative or potentially treatable as such depending on the degree to which their full scales occur in our study population. We will thus describe each initially as indicated above for quantitative baseline variables, overall and by treatment \times time combinations, including visually using grouped boxplots and kernel density estimators. To assess compatibility with the assumptions of the planned analytic approach, for each outcome we will use restricted (equivalently, residual) maximum likelihood (REML) estimation to fit preliminary mixed models with fixed effects of randomized treatment, visit, and their interactions, and with unrestricted covariance matrices -- thus allowing within treatment and visit variability to change over time and accounting for arbitrary correlations between measurements of the outcome in the same patient at different visits. These models will not be used to estimate treatment effects, but only to assess the compatibility of their residuals with the requisite distributional assumptions about random noise to support validity of fixed effect estimates and tests from the planned inferential analyses.

Estimated skewness, excess kurtosis, quantile-quantile (qq) plots, boxplots, and residual vs. predicted (for the six treatment \times time combinations) plots, particularly of Studentized and standardized residuals, will be used for this purpose. We will not use formal hypothesis tests of normality of the residual distributions, as the relevant issue is not whether the data literally arise from a normal distribution, which is virtually never the case, but rather whether the extent of departure from normality is enough to meaningfully distort effect estimates and associated hypothesis tests. Models based on Gaussian assumptions are robust to modest to moderate violations of assumptions, particularly to the distributional assumption when samples are reasonably large, in which case formal tests of normality may have power against small and often inconsequential departures from it.

For outcomes with distributional characteristics reasonably compatible with standard linear mixed model assumptions, we will employ prespecified linear mixed model analyses for the observations at baseline, six months, and twelve months, i.e., one year, as described below. For outcomes whose distributions, conditional on treatment and time, are substantially skewed and/or lighter or heavier tailed than Gaussian distributions (leptokurtotic or platykurtotic), we will consider applying the planned analysis to a Box-Cox and other reasonably straightforward data transformation of the outcome and backtransforming the results, and/or use of a generalized linear mixed model with log or other link function and/or a non-Gaussian exponential family or a beta error distribution. In exploring Box-Cox transformations, we will be generally guided by the independence pseudologlikelihood of the fitted fixed effects model saturated for treatment \times visit with clinical site as an additive covariate, as a function of the Box-Cox transformation power parameter. If and when transformations are used, we will report modeling results on the transformed scale and also report additive treatment effects, which for nonlinear transformations will vary by baseline value of the outcome, for selected percentiles of such baseline values. Nonparametric approaches such as quantile regression or product multinomial-based mixed categorical data models for marginal means will be considered as needed for bounded integer-scored outcomes with limited ranges and/or floor or ceiling effects, which may not admit of straightforwardly interpretable and communicable normalizing transformations.

Once the scale of analysis and analytic approach have been chosen for outcomes incompatible with the prespecified default model, a covariance structure will be selected for each non-multinomial analysis by comparing Schwarz' Bayesian Information Criterion (BIC) after fitting the unconstrained fixed effects model above using the following six choices: time series homogeneous and heterogeneous order one autoregressive AR(1), order one antedependence, homogeneous and heterogeneous compound symmetry, and unrestricted. The homogeneous AR(1) will be considered the default if it yields close to the minimum BIC; otherwise, the structure with minimum BIC will be used. Residuals from the above saturated fixed effects model with the selected covariance structure will then be checked as above to confirm adequacy of the transformation or generalized linear mixed model.

Treatment effect estimation and testing

Assuming required assumptions are reasonably met, missing data will be multiply-imputed with 50 imputations, as described above, after any transformations of all outcomes to the respective scales determined for analysis. Treatment effects will then be estimated and tested by fitting mixed models, also as described above, on the original or transformed scale, but assuming equally spaced visits and linear time effects, to each imputed full data set. Estimates of the annual rate of change of the outcome variable within each treatment group, and of the treatment effect as their difference, with respective standard errors, will be obtained from each imputation and combined over all imputations using Rubin's standard method, yielding overall point estimates of the rates in each group and the difference in rates between the home Peloton-based exercise and usual care groups (i.e., the treatment effect), with respective overall 95% confidence intervals. Statistical significance of the treatment effects and of temporal change within each group will be tested using Wald statistics. Point and interval estimates on a transformed scale will be back transformed and reported and interpreted on the scales of the original measurements as differences between model-fitted (“predicted”) values of the outcomes for participants beginning with the same baseline value of the outcome measure but assigned to the two groups, for a selection of baseline percentiles of the outcome measure (e.g., 5, 10, 25, 50, 75, 90, 95)..

To control the overall false positive rate of claiming disease-modifying therapeutic benefit from the home Peloton-based aerobic exercise program at 5% in the context of CYCLE II's nine inferential and other descriptive/exploratory outcomes, interpretation of significance testing will be in accordance with a prespecified outcome hierarchy. Specifically,

- i. overall benefit will only be claimed if the test of the primary UPDRS III outcome is statistically significant in the direction of exercise superiority at a two-sided $\alpha=5\%$,
- ii. benefit will only be claimed for a secondary motor inferential outcome if i) is satisfied and if the treatment effect is also statistically significant for that secondary motor outcome after Holm-Bonferroni adjustment for multiple testing of the five secondary motor outcomes; and
- iii. benefit will only be claimed for a secondary non-motor inferential outcome if i) is satisfied and if the treatment effect is also statistically significant for that secondary non-motor outcome after Holm-Bonferroni adjustment for multiple testing of the three secondary non-motor outcomes;
- iv. benefit will not be claimed to have been demonstrated based on estimated treatment effects on any variable other than the nine prespecified primary and secondary endpoints, and any associated p-values and confidence intervals for such other variables will be presented as descriptive only and potentially for guidance by designers of subsequent studies, and specifically noted to be unadjusted for multiple comparisons of over a dozen outcomes.

For inferential outcomes for which statistically significant treatment effects are found, in either direction, we will further explore the nature of the treatment effect. For the primary outcome and any descriptive/exploratory outcomes that are also indices of multiple Parkinson's disease manifestations and that exhibit clinically relevant differences between treatment group, we will summarize and compare subscores associated with different symptom groups, e.g., speech and facial expression, hand movements, lower body movements, tremor. For any outcome with statistically significant treatment effect, we will examine the effect in a model saturated for treatment and time, within which we will separately estimate and test equality of the changes within each six-month period, i.e., test for nonlinearity over the one-year duration of treatment and compare treatments with respect to the changes within each six-month period and over the full year of treatment.

Sensitivity analyses

We will employ several sensitivity analyses to test the dependence of substantive results on our modeling assumptions. Our planned analyses rely on randomization to protect against confounding by baseline differences between the treatment groups. We will compare treatment groups on the baseline variables mentioned above and perform covariate-adjusted sensitivity analyses based on material baseline

differences between them. For this purpose, we will consider variables with standardized differences exceeding 15% and/or variance ratios exceeding 2.0 for inclusion in these models. Any adjustments for continuous covariates will include linear as well as nonlinear representations of these variables using restricted cubic spline terms. To assess sensitivity to the imputation models, we will also compare results of analyses using multiply-imputed data with results based on complete cases and available cases and, for any outcomes with borderline results, to those from alternative imputation models. To assess sensitivity to the choice of data transformations and distributional assumptions, we will compare results to those of multinomial based categorical data mixed models for marginal mean scores.

Exploratory/descriptive outcomes

